### 3.2.3. Study Design and Methodology

This study has been designed as a randomized, double-blind, placebo-controlled, crossover study to reduce patient selection and assessment bias, and account for placebo effect and inter-subject differences in digital blood flow. Non-invasive assessment of the effect on digital blood flow following a single dose of study treatment was chosen as the primary objective for this POM study to ensure a reliable and objective initial evaluation of pharmacodynamic effects in the setting of SSc-RP (Wilkinson 2018). Patient-reported outcomes (PROs) designed to evaluate the frequency, duration, and severity of Raynaud's attacks, commonly used to evaluate real-world efficacy of pharmacotherapies in this setting, have not been included as primary efficacy assessment in this study due to short treatment duration.

Exposure to cold challenge was incorporated in the study design to allow for a dynamic assessment of digital blood flow under conditions similar to a common physiological trigger responsible for Raynaud's attacks in SSc (Pauling 2012). Digital blood flow will be assessed each Treatment Visit at Predose for 5 minutes at room temperature, and at Postdose prior to cold challenge for 5 minutes at room temperature and for 30 minutes following a cold challenge. Washout Periods between Treatment Visits are defined as a minimum of 72 hours, which is a sufficient period to ensure elimination of temanogrel, and up to approximately 7 days, to accommodate feasibility of multiple study visits for the study participants. Biomarkers related to

the mechanism of action of temanogrel (plasma serotonin concentration) as well as vascular injury and endothelial dysfunction will be evaluated to explore their relationship with digital blood flow and the PD effects of temanogrel, in order to provide additional mechanistic insights.

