## 9.2. Treatment Visits

Randomization can occur after confirmation of all inclusion and exclusion criteria at Check-in prior to the planned administration of study treatment on Treatment Visit 1.

Each subject will participate in 3 Treatment Visits, which will each be separated by a Washout Period of at least 72 hours and up to approximately 7 days between study treatment administrations. When possible, it is preferred to schedule Treatment Visits with the minimum possible Washout Period between visits. For each Treatment Visit, subjects will be admitted to the clinic at approximately the same time of the day (between 0800 and 1200 hours). A schematic of Treatment Day assessments and procedures is provided in Appendix 2. Refer to the Schedule of Assessments (Appendix 1) for additional details on study assessments and procedures.

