### **10.3.** Pharmacodynamic Assessments

#### 10.3.1. Digital Blood Flow Assessments and Cold Challenges

Assessments of digital blood flow based on both temperature and perfusion and will be conducted simultaneously using IR thermography (Section 10.3.1.1) and LSCI (Section 10.3.1.2), respectively. Digital blood flow data will be analyzed by a central core lab. Details on the applicable instructions regarding the collection, transfer, and analysis of blood flow data will be provided in a separate operation manual. Digital blood flow will be assessed at each Treatment Visit at Predose for 5 minutes at room temperature, and at Postdose prior to cold challenge for 5 minutes at room temperature and for 30 minutes following a cold challenge.

Digital blood flow will be assessed and analyzed as previously described (Wilkinson 2018) and details on the applicable methods can be found in separate operation manuals. Briefly, imaging should be performed at each Treatment Visit at approximately the same time of the day in a temperature-controlled (23 [ $\pm$  1]°C), low-lit room, and any vibrations (included those caused by walking or talking) should be minimized during the digital blood flow assessments. The room temperature should be assessed at least during the acclimatization and re-acclimatization periods, and after the post-cold challenge digital blood flow assessments have been completed. Subjects should be in a seated position during the digital blood flow assessments; standing up and walking

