for a minimum of 5 minutes before the start of imaging should be avoided. Hands should be placed at a fixed distance and angle from the thermal camera and LSCI and secured to avoid movement during imaging. Both hands will be used for digital blood flow assessments and cold challenges. Room temperature digital blood flow assessment will be performed following acclimatization for at least 20 minutes. For the cold challenge, hands will be placed in nitrile gloves (to prevent evaporative cooling) and immersed in a temperature-controlled water bath  $(15 [\pm 1]^{\circ}C)$  up to the radiocarpal joints for 1 minute ( $\pm$  3 seconds). The water temperature should be recorded at the beginning and at the end of the cold challenge. Immediately after the cold challenge, the gloves will be removed, the hands will be dried and returned to their original position on the insulating surface, and the post-cold challenge digital blood flow assessment will start 30 ( $\pm$  10) seconds after the end of the cold challenge.

ROIs on both hands will be predefined and the same ROIs will be used for analysis during all digital blood flow measurements for all subjects. Data will be presented in temperature (°C) for IR thermography or in arbitrary pu for LSCI and averaged for all ROIs. Absolute measurements (eg, room temperature values, maximum reduction/recovery) as well as dynamic assessments dependent on the characteristics of the rewarming/reperfusion curve (eg, AUC, time to 50% and 70% recovery [minimum value + (baseline value – minimum value)  $\times$  0.5 and minimum value + (baseline value – minimum value)  $\times$  0.7]) will be assessed.

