## **11.2.** Determination of Sample Size

Approximately 24 subjects are planned to be randomized in Stage A, which is sufficient to achieve at least 80% power to detect a treatment effect of 16.6% from placebo for change in digital blood flow based on rewarming AUC (°C, assessed with IR thermography) during the 30 minutes following a cold challenge for each of the 2 temanogrel treatments based on a difference of means test for a 3-period, 3-treatment crossover design with a significance level 0.05 (2-sided). The test assumes the temanogrel treatment group mean of 365, placebo group mean of 313, and an SD of the difference in temanogrel treatment and placebo group means of 86. In addition, with 24 subjects there is at least 80% power to detect a treatment effect of 23.5% from placebo for change in digital blood flow based on reperfusion AUC (pu, assessed with LSCI) during the 30 minutes following a cold challenge for each of the 2 temanogrel treatments (temanogrel treatment group mean of 24.7, placebo group mean of 20, and an SD of the difference in temanogrel treatment of 7.8). Assumptions are based on previous studies in SSc-RP utilizing these or similar methods (Herrick 2014, Wilkinson 2018,

Wise 2004). Subjects will be equally randomized (1:1:1:1:1:1 ratio) to 1 of the 6 treatment sequences (4 subjects per sequence).

Approximately 24 subjects are planned to be randomized in Stage B using the same 3-period, 3-treatment crossover design. Based on Stage A results, Stage B sample size may be modified, but not limited to, Stage A dose levels will be enriched or 2 additional temanogrel doses will be evaluated.

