## 11.5. Efficacy Analyses

The primary and secondary endpoints will be analyzed using the FAS. Other important statistical considerations and sensitivity analyses will be described in the SAP.

The primary endpoints of the study are the change in digital blood flow based on rewarming/reperfusion AUC (assessed with IR thermography and LSCI, respectively) during the 30 minutes following a cold challenge. The primary analyses will be analyzed using analysis of variance (ANOVA; Williams' design) with a model that includes treatment group, sequence, and period as factors. Least square means, standard errors (SEs), and 95% confidence intervals (CIs) for the treatments and their difference will be presented together with their p-values.

Unless otherwise specified, continuous secondary endpoints will be analyzed using ANOVA (Williams' design) with a model that includes treatment group, sequence, and period as factors. Least square means, SEs, and 95% CIs for the treatments and their difference will be presented together with their p-values.

Time-to-event secondary endpoints will be displayed using Kaplan-Meier plots and analyzed with Cox regression with a model that includes treatment group, sequence, and period as factors. The hazard ratio will be presented together with 95% CIs and the p-value.

Given subjects will receive all 3 treatments in 1 of 6 possible sequences, first-order carryover effects will be evaluated to assess the extent to which the order of treatments affected primary and secondary endpoints.

Details of the analysis methods for exploratory endpoints will be described in the SAP.

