#### **11.5.2.** Secondary Endpoints

- Change in the following temperature (°C, assessed with IR thermography) and perfusion (pu, assessed with LSCI) parameters:
  - Maximum reduction following a cold challenge
  - Maximum recovery during the 30 minutes following a cold challenge
  - AUC during the initial 2 minutes following a cold challenge
  - Slope during the initial 2 minutes following a cold challenge
  - Time to achieve 50% recovery from the cold challenge-induced reduction
  - Time to achieve 70% recovery from the cold challenge-induced reduction
- Change from Predose to Postdose in the following temperature (°C, assessed with IR thermography) and perfusion (pu, assessed with LSCI) parameters:
  - Room temperature values
  - Distal dorsal difference (DDD) (defined as the difference in measurements between the dorsum and the finger) at room temperature

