- n Room temperature digital blood flow is assessed at each Treatment Visit at Predose for 5 minutes and at Postdose for 5 minutes prior to the cold challenge.
- The cold challenge is conducted at each Treatment Visit at after Postdose room temperature (pre-cold challenge) digital blood flow assessments by immersing the hands in temperature-controlled water bath (15 [± 1]°C) for 1 minute (± 3 seconds). The post-cold challenge digital blood flow assessments will begin 30 (± 10) seconds after the completion of the cold challenge and last for 30 minutes.
- p Dosing is to occur at each Treatment Visit after completion of the Predose assessments.

q To be completed at each Treatment Visit at Postdose after completion of post-cold challenge digital blood flow assessments and blood draws.

ECG, electrocardiogram; eCRF, electronic case report form; IR, infrared; PK, pharmacokinetic

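### Optional efficiency gain: the same-visit Predose blood-flow value, recorded before dosing at all three visits, is not a covariate in the stated primary model

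*Combined protocol and SAP*

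**What the plan says.** **Model.** Section 11.5 and the Synopsis (Statistical Analysis) both give the primary analysis as a Williams-design ANOVA "with a model that includes treatment group, sequence, and period as factors". Neither names a covariate or a subject term. Section 11.5 leaves other statistical considerations and sensitivity analyses to the SAP.

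**Data available.** Section 10.3.1: "Digital blood flow will be assessed at each Treatment Visit at Predose for 5 minutes at room temperature". Thermography and LSCI are recorded simultaneously, and "the same ROIs will be used for analysis during all digital blood flow measurements". The Appendix 1 footnotes fix the order: "Dosing is to occur at each Treatment Visit after completion of the Predose assessments". The Predose value is therefore a true pre-treatment measurement for each period.

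**Stated use of Predose.** It appears by name only in the secondary endpoints of section 11.5.2: "Change from Predose to Postdose in the following temperature" and perfusion parameters, namely room-temperature values and the distal dorsal difference.

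**Design rationale.** Section 3.2.3 says that the randomized, blinded, placebo-controlled crossover is meant, among other things, to "account for placebo effect and inter-subject differences in digital blood flow". Visits are separated by "at least 72 hours and up to approximately 7 days between study treatment administrations" (section 9.2).

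**Planning figures.** For thermography, section 11.2 uses means of 365 and 313 and "an SD of the difference in temanogrel treatment and placebo group means of 86". For LSCI it uses 24.7 against 20 with an SD of 7.8. It claims at least 80% power with 24 subjects.

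**SAP.** The Note to File (Amendment 1) records it as draft v0.5. Its text is not in the file.

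**The concern.** Comparing treatments within subjects removes stable differences between people. It does not remove a subject's own variation from one visit to the next. In this trial the visits are days apart, and skin temperature and perfusion may differ on arrival. The same-visit Predose value is the only blood-flow measure taken before dosing that could account for that variation.

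If Predose tracks the visit-to-visit part of the AUC, adjusting for it narrows the primary intervals using data already collected. Writing the choice down in advance also prevents a choice between adjusted and unadjusted results after both have been seen. What is at stake is precision in a 24-subject proof-of-mechanism stage, not validity.

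**Working it through.** **1. Reproduce the stated power.** Inputs from section 11.2: N = 24, two-sided 0.05, thermography difference 365 − 313 = 52 with SD of the difference 86; LSCI 24.7 − 20 = 4.7 with 7.8.

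- SE = SD/√24: 86/√24 = 17.55; 7.8/√24 = 1.592.
- Paired t, 23 df: power 81.0% (thermography) and 80.7% (LSCI).
- Three-period crossover with subject effects: residual df = 72 observations − 24 subjects − 2 periods − 2 treatments = 44. Power is 82.6% and 82.3%.

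The claim of at least 80% is reproduced either way. The subject-effects model is the benchmark below, because an SD of the difference implies a within-subject comparison.

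**2. Add the covariate.** Let r be the within-subject correlation between the Predose value and the AUC. This is an assumption; the documents give no value.

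- SE with covariate = SE × √[(1 − r²)(1 + 1/42)], on 43 df. The factor 1 + 1/42 allows for chance imbalance in the covariate.
- Half-width = t × SE, with t = 2.015 on 44 df and 2.017 on 43 df.
- Example, thermography, r = 0.3: 17.55 × √(0.91 × 1.0238) = 16.94; 2.017 × 16.94 = 34.2.

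| | Without | r = 0 | r = 0.1 | r = 0.3 | r = 0.5 |
|---|---|---|---|---|---|
| Thermography power, % | 82.6 | 81.6 | 82.0 | 85.1 | 91.1 |
| Thermography half-width | 35.4 | 35.8 | 35.6 | 34.2 | 31.0 |
| LSCI power, % | 82.3 | 81.4 | 81.8 | 84.8 | 90.9 |
| LSCI half-width | 3.21 | 3.25 | 3.23 | 3.10 | 2.81 |
| Unadjusted N with the same power | 24 | 23.4 | 23.7 | 25.7 | 30.9 |

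Power with and without the covariate is equal at r = 0.156. The largest loss, at r = 0, is about 0.9 points. A simulation of the six-sequence, four-per-sequence design with subject effects gave the same pattern, with type I error of 4.7 to 5.0% with the covariate.

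**3. The model as literally listed.** With no subject term and independent errors, residual df = 72 − 1 − 5 − 2 − 2 = 62, or 60 with the covariate split into subject mean and visit deviation. The result now depends on two further unknowns: the between-subject share of variance (ICC) and the between-subject correlation of Predose with AUC. Simulated thermography half-widths at ICC 0.5:

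- Between-subject correlation 0: about 47.7 without; 48.1, 47.8, 47.1 and 45.2 with, at r = 0, 0.1, 0.3 and 0.5.
- Between-subject correlation 0.5, r = 0.3: about 47.5 to 44.0.
- Between-subject correlation 0.5, r = 0: about 47.7 to 45.8, so the interval narrows even with no within-subject link.

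At r = 0.3 the relative narrowing is 1 − 34.2/35.4 = 3.4% in the subject-effects model. In the literal model it is 1 − 47.1/47.7 = 1.3% with between-subject correlation 0, and 1 − 44.0/47.5 = 7.4% with 0.5. The gain can be smaller or larger than the benchmark.

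**4. Why a covariate and not a subtraction.** With equal SDs, subtracting Predose changes the variance from σ² to 2σ²(1 − r), which helps only if r exceeds 0.5. A covariate estimates the slope instead of fixing it at 1.

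**The case against.** A period-specific baseline covariate is optional in a crossover, and nothing in the file supports any value of r. Several features may make r small:

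- Visit conditions are already controlled: standard breakfast and avoidance of caffeine and alcohol (section 5.1), no vigorous exercise (5.2), similar dosing time (6.5), and a 23 ± 1°C low-lit room with seated subjects and fixed hand position (10.3.1).
- About 45 minutes, re-acclimatization and a cold challenge lie between the Predose reading and the AUC.
- Sections 11.2 and 11.5.1 do not give the AUC's reference level. If it is a same-visit value, some visit-level variation may already be removed.

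The SAP may also have covered the matter. Development has stopped, the database was locked on 13 October 2022, and the Note to File says that the SAP will not be finalized.

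All of this stands, and it limits the size and use of the gain. It does not change the fact that the model stated in two places omits a valid pre-treatment measurement. Efficacy is still to be analysed, separately from the clinical study report, so the choice can still be written down.

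A reader might go further and infer that the omission biases the treatment comparison or leaves Stage A underpowered. The documents do not support that: the unadjusted comparison is randomized, and the stated power is reproduced without the covariate. Nor can the 91.1% at r = 0.5 be taken as an expected benefit, since r is assumed.

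**Conclusion.** The point holds as a low-cost, optional improvement. It is not an error in the plan.

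In a subject-effects model with 24 subjects, thermography power moves by between about −0.9 points (r = 0) and +8.5 points (91.1 − 82.6, r = 0.5); at r = 0.3 it is +2.5 points. The break-even of about 0.16 and the worst-case loss of 0.9 points belong to that model only.

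For the model as section 11.5 literally lists it, a reader might infer that the gain is always smaller. That is so if Predose and AUC are uncorrelated between subjects; otherwise the gain can be larger. Whether a subject term was intended is a separate question.

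The conclusion rests on the section 11.2 planning figures and on assumed correlations and ICC. The SAP text could not be checked, so the finding concerns the protocol's stated model.

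**What to change.** - Prespecify the same-visit Predose room-temperature value of the same modality (°C for the thermography AUC, perfusion units for the LSCI AUC) as a covariate, not as a subtraction.
- Fit it in a model with subject effects, or split it into the subject mean and the visit deviation from that mean.
- Report the unadjusted result beside it, and state how a missing Predose value is handled.
- Do not adjust for the Postdose pre-challenge value. It is measured after dosing and may carry part of the treatment effect.
- If treatment codes are already open when this is written, label the adjusted result supplementary.

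**Cost.** Text in the SAP or in whatever document governs the separate efficacy analysis; one degree of freedom, or two if the covariate is split; and, in the subject-effects model, up to about 0.9 points of power if Predose proves uninformative. A visit with no Predose value drops out of the adjusted model unless the missing-data rule says otherwise. No new measurement is needed.

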# **3. STUDY DESIGN**

This is a Phase 2, multicenter, randomized, placebo-controlled, crossover study assessing the effect of oral temanogrel on digital blood flow in subjects with SSc-RP. The study will be conducted in 2 stages (Stage A and Stage B). Separate cohorts of subjects will participate in each stage. Subjects who participate in Stage A may not participate in Stage B. A study schematic is provided in Figure 1.

In Stage A, subjects will be equally randomized in a double-blind manner to a 3-period crossover treatment sequence. The Screening Period will last for up to 28 days prior to Day 1 (Treatment Visit 1). Each subject will participate in 3 Treatment Visits, which will each be separated by a Washout Period of at least 72 hours and up to approximately 7 days between study treatment administrations. During each Treatment Visit, subjects will receive a single dose of study treatment (placebo, 60 mg temanogrel, or 120 mg temanogrel) according to their crossover treatment sequence assignment.

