## **11.6.** Testing Strategy

No formal testing strategy or adjustments of the Type I error will be employed for the evaluation of secondary or exploratory endpoints. Estimates and 95% CI for treatment groups and from pairwise comparisons will be reported in an exploratory manner.

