# Note to File (Amendment 1)

Date:	28 October 2022	
To:	TMF	
From:	PPD	
Protocol No.:	APD791-204	
Subject:	Document the status of biometrics-related documents/processes and outline plan for select post-database lock safety and efficacy analyses	
Background:	
 
On 25 August 2022, the decision was made to discontinue development of the Arena cardiovascular programs, which includes APD791 (temanogrel). Enrollment into the ongoing clinical trial APD791-204 was terminated effective immediately and study team activities were reprioritized to focus and accelerate study close-out activities. For this study, the biostatistics, data management, and statistical programming deliverables and activities are outsourced to the clinical research organization (CRO) Medpace.
 
As a result of the immediate termination, the biostatistics aspects related to finalizing documents (e.g., statistical analysis plan [SAP]) and other downstream activities are either immature and/or have not been established. These tasks would take significant time and resources by both the Arena and Medpace team to finalize, which is not feasible given the accelerated study close-out timeline, which includes the database lock (DBL) which occurred on 13 October 2022.
 
	
Final Status:	
 
Statistical Analysis Plan
 
Draft SAP (v0.5)
 
Statistical Analysis Plan: Table, Listing, and Figure (TLF) Shells
 
	
	• Draft TLF specifications (v0.2)	
	
 
CDISC Specifications and Datasets (aCRF/SDTM/ADaM)
 
aCRF (dbCRF; based on protocol amendment v3.0)
 
SDTM: Specifications and datasets by 04 November 2022
 
ADaM: Draft specifications (development not yet begun)
 
	
	
 
Statistical Analysis Plan: Table, Listing, and Figure (TLF) Programming
 
Based on Programming Specifications (v1.0 dated 11 October 2022), the listings described in "Deliverables & Analyses" section will be produced.
 
	
	
 
Define.xml
 
Development has not begun for either SDTM or ADaM Defines
 
	

[figure not shown]

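### The Cox model for time to 50% and 70% recovery has no subject term or clustered variance, so its intervals and p-values ignore that each subject supplies three times

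*Combined protocol and SAP*

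**What the plan says.** Section 11.5.2 lists two time-to-event secondary endpoints, "Time to achieve 50% recovery from the cold challenge-induced reduction" and "Time to achieve 70% recovery from the cold challenge-induced reduction", each for skin temperature and for perfusion. Section 11.5 provides Kaplan-Meier plots and says that these endpoints are "analyzed with Cox regression with a model that includes treatment group, sequence, and period as factors". It adds: "The hazard ratio will be presented together with 95% CIs and the p-value".

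Section 3 states: "Each subject will participate in 3 Treatment Visits". Section 11.5 confirms that every subject receives all three treatments, and section 6.4 plans 4 subjects in each of 6 sequences. According to section 3.2.3, the crossover design was chosen partly to "account for placebo effect and inter-subject differences in digital blood flow".

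No section mentions a subject stratum, a frailty or a clustered variance. Section 11.1 leaves statistical detail to the SAP. The Note to File (Amendment 1) gives a draft, version 0.5, as the SAP's final status, and that draft is not among the documents. Under section 11.6, results for the secondary endpoints "will be reported in an exploratory manner".

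**The concern.** Three times from one subject are correlated if some subjects rewarm faster than others under every treatment. Sequence cannot stand in for subject, because each sequence holds four different subjects. A Cox model with only treatment, sequence and period takes its standard errors from the assumption that all the times are independent.

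In a crossover the treatment contrast is made within subjects. Ignoring positive correlation therefore tends to make the standard error too large: intervals are too wide and power is lost. If subjects hardly differ, that effect vanishes, and the five sequence coefficients fitted to a small data set push the other way. The reader of a hazard ratio, interval and p-value could not tell which case applies.

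There is also a question of estimand. When subjects differ, the marginal and within-subject hazard ratios are different quantities. That is not simply bias, but the plan does not say which one it will report.

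**Working it through.** **1. Data structure.** 24 subjects × 3 visits = 72 times per endpoint and modality. Two thresholds × two modalities = 4 endpoints.

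**2. The plan's own power figure.** The documents give no power, event count or hazard ratio for the Cox endpoints. For the primary AUCs, section 11.2 claims at least 80% power with n = 24 and two-sided α = 0.05. A paired t-test has noncentrality Δ/(SD/√n) on 23 df:

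- Thermography: Δ = 365 − 313 = 52, SD of difference 86. 52/(86/√24) = 2.96, power 81.0%.
- LSCI: Δ = 24.7 − 20 = 4.7, SD of difference 7.8. 4.7/(7.8/√24) = 2.95, power 80.7%.

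The claim reproduces. If the same SDs are used as single-arm SDs for two independent samples of 24, power is 55.4% and 55.1%. So the sample size rests on within-subject comparison, which the stated Cox model does not use.

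**3. Simulation of the planned Cox model.** From the protocol: 24 subjects, 4 per sequence, 3 periods, censoring at 30 minutes. Assumed: exponential times, placebo median 12 minutes, log-normal subject frailty, and both doses at hazard ratio 1 (type I error) or 2 (power). The test is high dose against placebo, two-sided at 5%, with 8,000 trials per setting (Monte Carlo SE about 0.2 to 0.3 points on type I error and 0.6 on power).

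The clustered alternative fits treatment and period. With I the information matrix and U_g the score total for subject g, its variance is I⁻¹(Σ U_g U_gᵀ)I⁻¹ × G/(G−1), referred to t on G−1 df. Here G = 24, so the factor is 24/23 and df = 23.

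| Assumed subject SD (log hazard) | 0 | 0.5 | 0.75 | 1.0 | 1.5 |
|---|---|---|---|---|---|
| Planned: model SE ÷ true sampling SD | 0.90 | 0.96 | 1.03 | 1.11 | 1.25 |
| Planned: type I error, % | 7.3 | 5.9 | 4.2 | 3.0 | 1.3 |
| Clustered, corrected: type I error, % | 5.4 | 5.4 | 5.1 | 5.0 | 5.0 |
| Planned: power, % | 66 | 55 | 46 | 36 | 20 |
| Clustered, corrected: power, % | 60 | 53 | 49 | 44 | 37 |
| Stratified by subject: power, % | 43 | 43 | 42 | 41 | 38 |

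- Stratified type I error is 5.6 to 6.0%. Clustering without the correction gives 6.6 to 7.3%.
- The 7.3% at SD 0 comes from the sequence coefficients; without them it is 5.3%.
- Dropping sequence without clustering makes matters worse where subjects differ: 1.7% at SD 1.0.
- With placebo medians of 6 or 20 minutes (3,000 runs each), planned type I error is 3.0% at SD 1.0 and 1.3 to 1.5% at SD 1.5.
- Repeat runs of 2,000 to 4,000 trials gave the planned model 6.5–6.8 / 5.1–5.7 / 2.8–3.2 / 1.4–1.5% at SD 0 / 0.5 / 1.0 / 1.5.

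**4. A different time distribution.** Assumed: lognormal times, median 8 minutes, SD of log time 0.9, total variance held fixed, 2,000 trials per setting. Power is for a log-time shift of 0.45 on one dose.

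| Within-subject correlation | 0 | 0.3 | 0.5 | 0.7 | 0.85 |
|---|---|---|---|---|---|
| Planned: model SE ÷ true SD | 0.88 | 0.98 | 1.09 | 1.30 | 1.64 |
| Planned: null rejection, % | 7.8 | 5.3 | 2.4 | 1.3 | 0.4 |
| Stratified: null rejection, % | 5.6 | 5.4 | 6.2 | 4.9 | 5.1 |
| Planned: power, % | 42 | 43 | 45 | 50 | 54 |
| Stratified: power, % | 30 | 43 | 54 | 78 | 95 |

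Under these times, repeat runs put the corrected clustered treatment-plus-period test between 4.3% and 7.0%, with the 7.0% at zero correlation.

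**5. Which hazard ratio.** With a true within-subject hazard ratio of 2.0 in the step 3 model, the median estimates at SD 1.0 are 1.72 (planned), 1.62 (clustered) and 2.09 (stratified). At SD 1.5 they are 1.56, 1.47 and 2.11. Clustering corrects the standard error; it does not turn a marginal hazard ratio into a within-subject one.

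**The case against.** The strongest reply is that section 11.5 lists factors, and a clustered variance is not a factor. The primary ANOVA is described by the same three terms, and the detail was deferred to the SAP, whose draft may have dealt with clustering. It is true that the contents of the draft are unknown. But the ANOVA sentence is tied to a named crossover design, which can imply a subject term, while the Cox sentence names none, and standard Cox software adds no within-subject structure unless told to. A deferral to a SAP that never became final does not fill the gap.

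Second, the subject variance is unknown. On the step 3 assumptions the planned test is near nominal at SD 0.5 to 0.75, and has more power than the clustered test at SD 0 to 0.5. This stands, although part of that advantage comes from rejecting more than 5% under the null. Part of the planned model's fall in power from 66% to 20% also reflects added total variance and a marginal hazard ratio nearer 1. With total variance fixed (step 4), planned power rises with correlation, but falls far behind the stratified test.

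Third, the practical weight is limited. The endpoints have no type I error control and no sample size rests on them. Development has stopped, and the Note to File keeps the imaging efficacy analyses out of the clinical study report. All of this stands. The same note says those analyses will still be conducted separately, so the specification still matters.

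**Conclusion.** The concern holds. As written, the Cox analysis gives standard errors, intervals and p-values that do not reflect three times per subject. Type I error at a nominal 5% lies between 7.3% and 1.3% over assumed log-hazard SDs of 0 to 1.5, and falls to 0.4% under lognormal times with correlation 0.85. If subjects differ appreciably the test is conservative and loses power: against the corrected clustered test, 44 − 36 = 8 points at SD 1.0 and 37 − 20 = 17 at SD 1.5. At SD 0.5 or below the standard errors are not too large. It should therefore not be described as a general inflation of type I error.

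The omission is plain from the text. The size rests on assumed medians, hazard ratio, time distribution and subject variance, with no dropout. The point should be corrected, but its reach is confined to exploratory secondary endpoints.

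**What to change.** State in the SAP, or in whatever document governs the separate efficacy analysis, which hazard ratio is wanted.

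- **Marginal:** fit treatment and period with a subject-clustered sandwich variance, multiply by G/(G−1), refer to t on G−1 df (G = number of subjects), and label the hazard ratio marginal. Clustering is the essential change. Keeping sequence with the corrected clustering gives 5.3 to 6.0% under exponential times but up to about 7.6% under lognormal times, so dropping sequence is safer.
- **Within-subject:** stratify by subject or use a subject frailty. The frailty was not simulated.

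Keep the Kaplan-Meier curves descriptive.

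The cost is two lines of text, one option in the code and a short added calculation for the correction. On the step 3 assumptions, corrected clustering gives up 66 − 60 = 6 points of power if subjects do not differ at all and 55 − 53 = 2 at SD 0.5, and its hazard ratio stays nearer 1 than the within-subject one. Stratifying loses subjects with no event and gives up 66 − 43 = 23 points at SD 0 and 55 − 43 = 12 at SD 0.5; it overtakes the planned model only from about SD 1.0.
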